**Brief Psychiatric Rating scale (Overall & Gorham 1962)**

Is a widely used scale for the assessment of symptoms of schizophrenia and schizophrenia spectrum disorders. The scale has 18 items rated on a 7-point scale from not present to 7 extremely severe. It has good psychometric properties in terms of reliability and validity and sensitivity (Hedlund & Viewag, 1980). BPRS score of 31 corresponds to “mild illness”; 41 “moderately ill” and 53 “markedly “markedly ill” ( Leucht et al 2005).

**Behavioural Inhibition System/ Behavioural Activation System (BIS/BAS).** The BIS/BAS is a self-report scale measuring behavioural inhibition and activation (Demianczyk, Jenkins, Henson, & Conner, 2014). The questionnaire uses a 5-point Likert type response scale with 1 strongly disagree, 2 Disagree, 3 Neutral, 4 Agree, and 5 Strongly agree.

**fMRI Measures:**

Structural and functional MRI images are acquired by a 3T Siemens Magnetom TrioTim system using a 12-channel head coil. The sequences acquired and their parameters are as follows:

**T1-weighted imaging:** MP2-RAGE sequence. Time to acquire image: 5:02, Inversion 1: 700ms, Inversion 2: 2220ms, repetition time (TR): 4000 ms, echo time (TE): 2.96 ms, Voxel size: 1 mm isotropic, FoV= 230 mm, 192 slices with full brain coverage,;

**T2-weighted imaging.** Fluid Attenuated Inversion Recovery (FLAIR) sequence, time to acquire image: 2:44, Repetition Time: 9000ms, Echo Time: 81ms, Inversion Time: 2500ms, Flip Angle: 150 degrees, voxel size: 0.72 x 0.72 x 5.2mm. 30 Slices with full brain coverage.

**fMRI imaging.** Functional T2\*-weighted BOLD images are acquired using a multiband, echo-planar sequence, across the whole brain (TR: 0.628 ms, TE: 30 ms, resolution: 2.4 mm isotropic, FoV: 192 mm, flip angle: 52 degrees). 54 slices with full brain coverage. During fMRI imaging, participants will complete a computerised experimental task (see below). For each task condition, approximately 720 full brain images will be acquired, providing 1440 volumes acquired in approximately 12 minutes.

**Diffusion weighted Imaging.** A NODDI (Neurite Orientation Dispersion and Density Imaging) sequence with two shells and 90 gradient directions (B1=1000 with 30 directions, B2=2500 with 60 directions) with 6 B0 measurements will be acquired in the AP phase encoding direction, and an additional 6 B0 measurements will be acquired in the PA phase encoding direction. Total acquisition time: 7:24. Time of Repetition: 4100ms, Echo time: 75ms, voxel size: 2mm isotropic, 68 slices with full brain coverage.

**Susceptibility Weighted Imaging (SWI):** Time to acquire image: 2:56, RepetitionTime: 27ms, EchoTime: 20ms, flip angle: 15 degrees, voxel size: 0.89 x 0.89 x 2.5mm. 64 slices with full brain coverage.

**Experimental Task:**

During functional MRI imaging, participants will complete a computerised experimental task. This is a simple reinforcement learning task with two conditions, a social reward condition and a non-

social reward condition (see figure 1 below). Participants view an image on a computer screen, a leaking bucket on the non-social condition, and a face in the social condition. The goal is to fill the bucket with water (non-social condition) or to make the person smile (social condition). Three button responses are available to achieve these goals, represented on the screen by a square (left button), diamond (middle button) and pentagon (right button). Participants are told that one of these will; probably be a good choice (fills bucket or increases smile), while other choices may be poor choices (opposite effect). They must try to learn which buttons are the best responses by trial and error. The reward probabilities of each choice evolve over time however, requiring participants to continually track choice outcomes, and switch buttons over time to achieve their goal. Participants are encouraged to make button presses as quickly as possible (about 2-4 presses per second). Buttons A, B and C are randomly assigned to each reward probability for each task block. There are 10 blocks in each condition (social and non-social conditions). Blocks range from 20 to 45 seconds in length, allowing for hundreds of button choices per block, and thousands per condition. Completing both task conditions takes approximately 12 minutes. The task was developed by [name] for this study, and implemented in Matlab (Mathworks) using the Cogent 2000 toolbox (Wellcome Department of Imaging Neuroscience, Queen Square, London). During the fMRI experiment the task was seen by participants through a tilted mirror attached to the head coil on the MRI scanner. Responses were made on a commercially available MR-compatible response box(Current Design, <https://www.curdes.com/>).

**Fig. 2**

Schematic diagram for the reward learning experimental task. Left Panel: Non-social reward condition, Right Panel: Social reward condition. Top: Four choices are illustrated in each condition, with progress towards the goal from left to right (filling the bucket or making the person smile). Middle: The reward probabilities are identical in the social and non-social learning conditions. At each point in time there is one optimal button choice, and reward probabilities of each choice change during each task block. Bottom: The actual choices of a test participant are illustrated, and the value of each button calculated, based on the feedback available to that participant. While the non-social choices are close to optimal, learning in the social condition is less efficient. Participants are familiarised with the task and perform two blocks of each condition prior to brain scanning.

## **5. Study Restrictions**

Nil.

## **6. Safety Assessments**

All clinical patients recruited in this study will be registered patients of Metro South Addiction and Mental Health service. The study team will liaise with clinical staff to ensure that there are no unforeseen contraindications to the participant being involved. The experience of the MSAMHS since 2010 with the therapy, is that CIRCuiTS is seen as safe and there is no evidence that it is associated with an increased risk of adverse events. Patients with psychosis have often had head scans. A member of the research team will support the person during the fMRI scans.

## **7. Adverse Events (AE) and Serious Adverse Events (SAE)**

All adverse events reported between consent and final follow-up will be recorded. The investigator or designee will ask the Participant non-leading questions to detect adverse events e.g. “How have you been over the last 5 weeks”. We expect that adverse events will occur during the study related to fluctuations in the underlying mental disorder and medications. The investigator is responsible for the detection and documentation of events meeting the criteria and definition of an adverse event (AE) or a serious adverse event (SAE) as provided in this protocol. During the study, when there is a safety evaluation, the investigator or site staff will be responsible for detecting AEs and SAEs, as detailed in this section of the protocol

### **7.1 Definition of a Serious Adverse Event (SAE)**

A serious adverse event is any untoward medical occurrence that, at any dose:

- a) results in death
- b) is life threatening
- c) requires hospitalisation or prolongation of an existing hospitalisation.
- d) results in disability/incapacity, or
- f) Any event deemed by the investigator as being a significant medical event.

## 7.2 Time Period, Frequency, and Method of Detecting AEs and SAEs

All adverse events will be recorded between the time of consent and the follow-up visit. Each Participant will be monitored regularly by the investigator and study personnel for adverse events occurring throughout the study. The research team will enquire about AEs by asking the following non-leading questions:

At the first scheduled visit (baseline) participants will be asked:

*“How are you feeling?” Does your current treatment cause you regular side effects? Do you have any general health conditions that cause you problems on a regular basis (e.g. that we might expect to occur over the duration of this study?)”*

At subsequent scheduled visits, participants will be asked:

*“Since your last visit, have you had any health problems?”*

## 7.3 Recording of AEs and SAEs

If an AE/SAE occurs, the investigator will review all documentation (e.g. hospital progress notes, laboratory, and diagnostic reports) relative to the event. We will then record all relevant information regarding an AE/SAE in to the CRF, and code the AE according to industry standard MEDDRA coding rules.

## 7.4 Assessment of Intensity / Evaluating AEs and SAEs

The investigator will assess intensity for each AE and SAE reported during the study. The assessment will be based on the investigator’s clinical judgement. The intensity of each AE and SAE recorded in the CRF should be assigned to one of the following categories:

**Mild:** An event that is easily tolerated by the Participant, causing minimal discomfort and not interfering with everyday activities.

**Moderate:** An event that is sufficiently discomforting to interfere with normal everyday activities.

**Severe:** An event which is incapacitating and prevents normal everyday activities.

An AE that is assessed as severe should not be confused with an SAE. Severity is a category utilised for rating the intensity of an event; and both AEs and SAEs can be assessed as severe. An event is defined as “serious” when it meets one of the pre-defined outcomes as described in “Definition of an SAE”.

## 7.5 Assessment of Causality

The investigator is obligated to assess the relationship between investigational product and the occurrence of each AE/SAE. The investigator will use clinical judgment to determine the relationship. Alternative causes, such as natural history of the underlying diseases, concomitant therapy, other risk factors, and the temporal relationship of the event to the investigational product will be considered and investigated. The investigator will also consult the CIB and/or product information in the determination of his/her assessment.

The causal relationship to the study product assessed by the Investigator (or medically qualified delegate) should be assessed using the following classifications:

**Not Related** In the Investigator's opinion, there is not a causal relationship between the study product and the adverse event.

**Unlikely** The temporal association between the adverse event and study product is such that the study product is not likely to have any reasonable association with the adverse event.

**Possible** The adverse event could have been caused by the study Participant's clinical state or the study product.

**Probable** The adverse event follows a reasonable temporal sequence from the time of study product administration, abates upon discontinuation of the study product and cannot be reasonably explained by the known characteristics of the study Participant's clinical state.

**Definitely** The adverse event follows a reasonable temporal sequence from the time of study product administration or reappears when study product is reintroduced.

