#### **3.1 Interventions**

**CIRCuiTs (Computerised Interactive Remediation of Cognition – Training for Schizophrenia).** This is a modular computer package including tasks of a wide range of cognitive functions (particularly executive function and memory). CIRCuiTs are run for 1 hour twice a week for 12 weeks and is delivered through a computer. CIRCuiTS consist of 40 stages. Twenty sessions are considered an adequate treatment exposure and 20 minutes a “session”.

In this study 20 participants with schizophrenia (intervention group) will have one face to face meeting with the therapist to orientate to the program. These participants will then complete the program (40 sessions or 12 weeks of at least 20-minute session twice a week) either online or in-

person, and independently or in a group. The therapist will have telephone (duration <1 hour) contact once a week to support online participation. Only the intervention group will complete these sessions.

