						
assessment and managing high risk situations.
 
Research staff will have access to a clinically trained senior staff including a Project Manager and Chief Investigator who will assist research staff to conduct risk assessment and implement risk management plan if required i.e. notifying treating team and assisting in the participant accessing appropriate support (e.g. emergency services)
 
Previously identified high risk patients and recent risk assessments will be discussed at weekly team meetings and their management reviewed by senior research staff (including Project Manager and Chief Investigator).

--	--	--	--	--	--	---

						
Research staff will be given support and feedback on risk assessments and their management to improve skills throughout the project.

5.	
Transporting participants in QLD Health work vehicles
	
Research staff will be transporting participants to pathology appointments and may be required to transport participants to the interview site.
 
There may be risk associated with motor vehicle accident
 
There may be risks associated with unpredictable behaviour of a patient whilst being transported.
	Possible	Minor-Moderate	Medium -High	
Research staff will have a current QLD Driver’s Licence and completed the mandatory Driver Safety E-Learning Course.
 
Recruitment of experienced mental health clinicians who will be able to and manage unpredictable behaviour.
 
Research staff will carry a mobile phone and adhere to a sign in/out policy and advise the Project Manager of the address they will be attending.

6.	Psychological discomfort during MRI	Participants may become distressed (for example as a result of feeling claustrophobic) within the MRI.	Possible	Minor – Moderate	Medium-High	
Screening – advised and asked if this is likely.
 
Discussed again at the time of screening. Also advised MRI can be ended if this occurs. Advised of emergency button to press in this instance.
 
Checked on during the MRI by radiographer using intercom system. The participant is then able to advise if they are becoming distressed.

7.	Risk of physical harm during MRI	If a participant undergoes an MRI with metal in their body this can result in physical harm to the participant (i.e. the implant may cease to	Possible	Major	High	A strict metals check procedure will be followed to mitigate the risk of scanning a participant with metal in their body. Three metal checks will occur;

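### Section 7.5 rates adverse-event causality only against an undefined study product, so it cannot record that the MRI, an assessment or study transport caused an event

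*Protocol*

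**What the plan says.** Section 7.5 requires a causality judgement for every event: "The investigator is obligated to assess the relationship between investigational product and the occurrence of each AE/SAE". The scale is introduced with the same object: "The causal relationship to the study product assessed by the Investigator (or medically qualified delegate) should be assessed using the following classifications". Each category keeps it. *Not Related* means that "there is not a causal relationship between the study product and the adverse event", and *Unlikely* means that "the study product is not likely to have any reasonable association with the adverse event". *Possible* covers an event that either the participant's clinical state or the product could have caused. *Probable* and *Definitely* refer to the timing of the product's administration, and to the event abating when it stops or returning when it is given again.

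Other causes enter only as competing explanations: "Alternative causes, such as natural history of the underlying diseases, concomitant therapy, other risk factors". Study procedures are not named among them. The reference material is also that of a product trial: "The investigator will also consult the CIB and/or product information in the determination of his/her assessment".

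The protocol does not define the product. Section 3.1 describes one intervention, the CIRCuiTS computer program, and adds: "Only the intervention group will complete these sessions".

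The risk plan in Section 7.7 lists harms that arise from study procedures. On the scanner it says: "If a participant undergoes an MRI with metal in their body this can result in physical harm to the participant". Section 8 requires of healthy controls only the fMRI task.

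**The concern.** The wording of Section 7.5 is that of a drug trial. This study gives most participants no product and exposes all three groups to imaging. Section 6 describes CIRCuiTS as safe, with no evidence of added adverse events, while the risk plan assigns Medium to High ratings to several procedures. Relatedness is therefore rated for the exposure from which the protocol expects little harm, and not for those where it does expect some.

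At stake is whether the causality data can answer a basic safety question: did taking part in the study, as distinct from the illness or usual care, cause the event? For an event in the scanner, an interview or a study vehicle, the scale as written cannot say yes.

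**Working it through.** **Head count.** Inputs: intervention group 20 (Section 3.1), treatment as usual 20 (Section 3.2.1), healthy controls 20 (Section 3.2.2).

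- Total: 20 + 20 + 20 = 60, which agrees with Section 3.3.
- Not planned to receive CR: 60 − 20 = 40, and 40/60 = 66.7%.

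**Never exposed to CR.** Under Section 3.2.1, people who start CR but do not complete more than 5 sessions are moved to treatment as usual, and those who can no longer complete CR may be offered that group. Let k of the 20 treatment-as-usual participants have had at least one session before moving, with group sizes as planned. The number never exposed is then 40 − k.

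- k = 0: 40 − 0 = 40.
- k = 20: 40 − 20 = 20, the healthy controls alone.

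**Number of scans.** The schedule figure is not shown, so this is an assumption.

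- Two scans per patient and one per control: 40 × 2 + 20 × 1 = 100.
- Two scans for everyone, as the three-group by two-time analysis in Section 9.2 would imply: 60 × 2 = 120.

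None of these 100 to 120 scans has a category that can state a causal link.

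**Risk plan against scale.**

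| Source of harm (Section 7.7) | Rating | Category in 7.5 that names it |
|---|---|---|
| Clinical and cognitive assessments (risk 1) | Medium | none |
| Transport (risk 5) | Medium-High | none |
| Distress in the MRI (risk 6) | Medium-High | none |
| Physical harm in the MRI (risk 7) | High | none |

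**Worked case.** Suppose a healthy control is hurt in the scanner and the investigator is certain that the scan was the cause. Section 7 records adverse events without limiting them to a group, and Section 7.5 demands a rating for each. There was no product, so *Not Related* fits by definition and *Unlikely* is the nearest alternative. *Probable* and *Definitely* presuppose that a product was given.

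For a patient who panics in the scanner, *Possible* could be used, because clinical state alone satisfies it. That attributes the event to the illness, not to the scan.

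**The case against.** The strongest reply is that little is lost. Sections 7 and 7.2 record all adverse events from consent to follow-up. Section 7.3 has the investigator review the documentation and enter the relevant information, Section 7.4 grades intensity, and Section 7.6 follows events to resolution or stabilisation. A scanner cause can be considered among the other risk factors in Section 7.5. MRI risks also have their own controls, including exclusions, an emergency button, an intercom and three metal checks. All of this stands: detection does not depend on the causality scale. It does not supply the missing category, and a procedure treated as an alternative cause counts against relatedness instead of being recorded as a form of it.

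A reader might also infer more than the documents support:

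- *Procedure harms must be rated Not Related.* No rule says so. *Unlikely* is available, *Possible* admits clinical state alone, and the rating rests on clinical judgement.
- *Forty participants never receive CR.* That is the planned count and an upper bound, given the re-allocation in Section 3.2.1.
- *Ethics committee reports would show these events as unrelated.* Sections 9.2.2 and 11 require at least annual reports but do not say that they are broken down by causality.
- *The scale misses the harms that the protocol rates highest.* Suicidal ideation (risk 4) is also rated High and is not a procedure harm.
- *No product information exists for CIRCuiTS.* The protocol does not show this either way.

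**Conclusion.** The point holds as a defect of attribution. Section 7.5 obliges a causality rating for each event but offers no means of linking an event to the MRI, the assessments or study transport, which Section 7.7 rates Medium to High. It affects all three groups, and most clearly the 20 healthy controls, for whom the scan is the main study exposure and CR exposure is certainly nil.

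The conclusion assumes that CIRCuiTS is the study product, since the protocol names no other candidate. The range of 20 to 40 participants never exposed to CR assumes that the planned group sizes are met; the scan count rests on the unseen schedule. Neither figure is needed for the core point, which follows from the wording of the scale. The protocol ties no endpoint, analysis or stopping rule to the rating, so the consequence is confined to safety attribution. It is worth correcting because the rule is stated in the protocol, misdirects attribution when followed, and is easily repaired.

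**What to change.** In Section 7.5:

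1. Replace the references to an investigational or study product with the CR intervention, CIRCuiTS, named explicitly.
2. Add a separate rating of relatedness to study procedures (MRI, clinical and cognitive assessments, study transport), completed for events in all three groups.
3. Reword the drug-trial terms (administration, reintroduction, CIB and product information) so that they fit a computer-based therapy and one-off procedures such as a scan.
4. Name study procedures where the section discusses causes, and bring it into line with the risk plan in Section 7.7.

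The cost is a wording change and one or more added items on the adverse-event form, depending on whether procedures are rated together or separately. A few more events may be reported as study-related. No treatment or clinical rule changes.

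### In Section 7.5 the causality category Definitely is easier to meet than Probable, so the top two categories overlap and stand in the wrong order

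*Protocol*

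**What the plan says.** Protocol Section 7.5 obliges the investigator to judge the relationship of every AE and SAE to the product, using five categories listed from *Not Related* up to *Definitely*. Three of them matter here.

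- *Possible*: "The adverse event could have been caused by the study Participant's clinical state or the study product".
- *Probable*: the event "follows a reasonable temporal sequence from the time of study product administration, abates upon discontinuation of the study product", and in addition it "cannot be reasonably explained by the known characteristics of the study Participant's clinical state". All three conditions must hold.
- *Definitely*: the event "follows a reasonable temporal sequence from the time of study product administration or reappears when study product is reintroduced". Either condition is enough, because the second is joined on as an alternative: "or reappears when study product is reintroduced".

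Ahead of the list, the section says: "The investigator will use clinical judgment to determine the relationship". It also asks that alternative causes be considered, among them the natural course of the underlying illness.

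Section 7 says what kind of events the sponsor foresees: "We expect that adverse events will occur during the study related to fluctuations in the underlying mental disorder and medications".

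**The concern.** On a rising causality scale, each step should demand at least as much evidence as the one below it. Here the top step drops two of the three conditions of the step beneath it and makes the remaining one sufficient by itself.

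One of the dropped conditions is the one this study most needs. Section 7 expects events that come from fluctuation of the illness and from medication. What separates such an event from one caused by the intervention is whether the clinical state explains it. That test is part of *Probable* and is absent from *Definitely*. CR sessions are planned twice a week for 12 weeks (Section 3.1), so an illness fluctuation may well fall in plausible sequence with a session. As the definitions are worded, one such event could be rated *Possible* by one assessor and *Definitely* by another, with both following the text. What is at stake is the consistency and meaning of the causality ratings in the CRF.

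**Working it through.** The protocol gives no figure to reproduce, so this is a check of logic.

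**Inputs, all from Section 7.5.** Four yes/no features of an event:

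- T: reasonable time sequence
- D: abates on discontinuation
- A: not reasonably explained by the participant's clinical state
- R: reappears on reintroduction

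Four features give 2 × 2 × 2 × 2 = 16 patterns.

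**Step 1. Probable as written = T and D and A.** R is free, so 2 of 16 patterns qualify.

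**Step 2. Definitely as written = T or R.** It fails only when both T and R are absent, which leaves D and A free: 2 × 2 = 4 patterns. So 16 − 4 = 12 of 16 qualify.

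**Step 3. Inclusion.** Both *Probable* patterns have T, so both are among the 12. *Probable* lies strictly inside *Definitely*, and 12 − 2 = 10 patterns meet *Definitely* without meeting *Probable*. The pattern with T only (D, A and R all absent) is one of those 10. It describes an event that is plausibly timed, did not abate on stopping, is explained by the clinical state and did not recur.

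**Step 4. Would changing *or* to *and* be enough?** T and R leaves D and A free: 4 of 16 patterns. Only the one with D and A both present also meets *Probable*; the other 3 of the 4 fail it. The order is still not restored.

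**Step 5. All conditions together.** T and D and A and R is 1 of 16 patterns and lies strictly inside the 2 *Probable* patterns. Among the three wordings compared here, this is the only one that makes *Definitely* stronger than *Probable*.

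| Wording of Definitely | Patterns met | Inside Probable? |
|---|---|---|
| T or R (as written) | 12 of 16 | No; it contains Probable |
| T and R | 4 of 16 | No; 3 of the 4 fall outside |
| T and D and A and R | 1 of 16 | Yes, strictly |

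The patterns are not equally likely and carry no weights. The counts show which definition contains which, and nothing about how many events would be misrated.

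**The case against.** The best defence is that the scale is not a mechanical algorithm. The section puts clinical judgement first and requires alternative causes to be considered. *Not Related* rests wholly on the investigator's opinion, and *Possible* expressly allows for the clinical state. An investigator can therefore properly rate an illness fluctuation in a lower category. This stands to the extent that the wording permits misclassification and does not compel it. It does not rescue the definition: the section goes on to direct that causality be assessed with the listed categories, and an assessor who declines *Definitely* on grounds of judgement is working around the written criterion.

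A reader might infer three stronger things, none of which the protocol supports.

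- *That any event following a session is definitely related.* The text asks for a reasonable time sequence, which is a judgement about plausible onset. Merely occurring later is not enough.
- *That relatedness counts sent to the ethics committee would be unusable.* Sections 9.2.2 and 11 promise at least annual reports but do not say that they tabulate events by causality. Section 9.2 contains no adverse event analysis.
- *That the counts would be inflated in the CR group only.* No tabulation by group is stated. Under Section 3.2.1, participants who start CR but do not complete more than 5 sessions move to the treatment-as-usual group, so exposure is not confined to one group.

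It is also fair to say that few related events may arise. About 20 participants receive CR, and Section 6 reports no evidence of increased risk with the program.

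**Conclusion.** The point holds as an error in an operative definition. As written, *Probable* and *Definitely* overlap and are in the wrong order: all *Probable* events also meet *Definitely*, and the converse fails. An event that is plausibly timed but explained by illness fluctuation could be rated *Definitely* under the definition.

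This rests on reading the conjunctions in Section 7.5 in their ordinary sense and on taking the five categories as a rising scale, which their names and order indicate. It does not depend on any assumed event rate.

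The consequence is minor and confined to adverse event causality classification. Withdrawal by the investigator (Section 8.1) turns on hospital admission or on capacity for ongoing consent, follow-up of events (Section 7.6) applies whatever the causality rating, and no efficacy analysis uses the scale.

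**What to change.** Reconcile the two definitions so that *Definitely* is strictly stronger than *Probable*: require all three *Probable* conditions and, in addition, reappearance on re-exposure. Replacing *or* with *and* in the present sentence is not sufficient, because abatement and the absence of another explanation would still be missing. This changes how an event is labelled; it neither asks for nor implies any decision to stop or resume sessions.

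State in the same section that the study product means the CR sessions, since the intervention is a computer program and the present wording is that of a medicinal product.

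Assess relatedness to MRI procedures separately, without the abatement and re-exposure conditions. Those conditions fit repeated sessions but not a single scan, and applying them there could bar an evident procedure-related event from the upper categories.

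The cost is about one sentence for the definition, a short clarification of terms and MRI events, and matching CRF guidance. The downside is that fewer events will be rated *Definitely*.
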